### **3.5 Duration of Follow Up:**

**30-Day Follow-Up:** Patients will be followed *for toxicity* for 30 days after treatment has been discontinued or until death, whichever occurs first.

**Long term Follow-Up:** Patients will be followed *for survival* every 3 months until death after discontinuation of study medications.

The clinical course of each event will be followed until resolution, stabilization, or until it has been determined that the study treatment or participation is not the cause.

Serious adverse events that are still ongoing at the end of the study period will necessitate follow-up to determine the final outcome. Any serious adverse event that occurs after the study period and is considered to be possibly related to the study treatment or study participation will be recorded and reported immediately.

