### **3.6 Replacement of Subjects**

Subjects who do not obtain the two MRI scans (baseline and 12 weeks) will be considered not evaluable for response and will be replaced.

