### **10.1.1 Treatment Period**

Treatment cycles are 21 days long.

A visit window of up to 3 days before treatment is allowed for chemistry, coagulation and hematology labs.

A visit window of  $\pm$  7 days is allowed for 3 month MRI/CT scans and follow-up visits.

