#### **11.1.1 Definitions**

Evaluable for toxicity All patients will be evaluable for toxicity from the time of registration to protocol.

Evaluable for objective response Only those patients who have measurable disease present at baseline, have received eribulin as per the protocol, and have had their disease re-evaluated will be considered evaluable for response. These patients will have their response classified according to the definitions stated below. (Note: Patients who exhibit objective disease progression prior to the end of cycle 1 will also be considered evaluable.)

Evaluable Non-Target Disease Response Patients who have lesions present at baseline that are evaluable, but do not meet the definitions of measurable disease, have received at least one cycle of therapy, and have had their disease re-evaluated will be considered evaluable for non-target disease. The response assessment is based on the presence, absence, or unequivocal progression of the lesions.

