### **11.2.1 Definitions**

Evaluable for toxicity: All subjects will be evaluable for toxicity from the time of their first treatment with eribulin.

Evaluable for objective response: Only those subjects who have measurable disease present at baseline, have received at least one cycle of therapy, and have had their disease re-evaluated will be considered evaluable for response. These subjects will have their response classified according to the definitions stated below.

**Note:** Subjects who exhibit objective disease progression prior to the end of cycle 1 will also be considered evaluable.

Evaluable Non-Target Disease Response: Subjects who have lesions present at baseline that are evaluable, but do not meet the definitions of measurable disease, have received at least one cycle of therapy, and have had their disease re-evaluated will be considered evaluable for non-target disease. The response assessment is based on the presence, absence, or unequivocal progression of the lesions.

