### **Evaluability**

To be evaluable for inclusion in the primary objective and secondary objectives, patients must have baseline and week 12 MRI.

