#### **Secondary Objective 2.2.2:** Toxicity

We will evaluate rates (and 95% CI) of toxicity in patients treated with eribulin.

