#### **Secondary Objective 2.2.5:** Overall Survival

We will generate a Kaplan-Meier curve of OS. Point estimates (and standard error) of OS will be calculated.

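### The week-12 MRI condition covers every secondary objective, so as written it removes early deaths from the overall survival curve and conflicts with the toxicity populations defined elsewhere

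*Combined protocol and SAP*

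**What the plan says.** Section 2.2 lists toxicity (2.2.2) and overall survival (2.2.5) among the secondary objectives. The Evaluability paragraph of Section 13.0 then sets one condition for all of them: "To be evaluable for inclusion in the primary objective and secondary objectives, patients must have baseline and week 12 MRI". It makes no exception.

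For OS, Section 13.1 says "We will generate a Kaplan-Meier curve of OS" and adds point estimates with standard errors. It gives no analysis population and no time origin. Section 3.5 plans survival follow-up "every 3 months until death after discontinuation of study medications", with no MRI condition. Section 3.6 is narrower than the Evaluability paragraph: patients without both scans "will be considered not evaluable for response and will be replaced".

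For toxicity there are three other statements:

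- Section 11.1.1: "All patients will be evaluable for toxicity from the time of registration to protocol".
- Section 11.2.1: "All subjects will be evaluable for toxicity from the time of their first treatment with eribulin".
- Section 13.1, Objective 2.2.2: rates "of toxicity in patients treated with eribulin".

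None of the three mentions an MRI.

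On timing, Section 10.1.1 gives a window: plus or minus 7 "days is allowed for 3 month MRI/CT scans and follow-up visits". The earliest in-window scan is therefore day 77 (week 11).

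**The concern.** Having a week-12 scan requires being alive to be scanned. If that is a condition for entering the OS analysis, no patient in the analysis can die before the scan, and the curve is flat at 100% up to that point by construction. This is immortal time: reported survival rises with no drug effect. The resulting OS would be conditional on surviving about three months, and it could not be read against the background survival figures in Section 1.4, which the plan uses to describe this population.

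For toxicity the problem is different. The analyst is given incompatible denominators. If the Evaluability paragraph were the one followed, patients who died early or stopped early without a scan would be dropped. That would be selection rather than immortal time. The documents do not show that it would happen, so this part is an inconsistency and not an established understatement.

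OS is descriptive here, and the success rule of 8 of 20 progression free at three months does not use it. What is at stake is the reported OS estimate and a clear toxicity denominator, not the primary decision.

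**Working it through.** **Which rule governs.**

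| Objective | Evaluability paragraph, 13.0 | Other statements | Result |
|---|---|---|---|
| OS (2.2.5) | Baseline and week-12 MRI required | 13.1 names no population; 3.5 follows survival to death; 3.6 limits the consequence to response | Nothing exempts OS, so the MRI condition applies as written |
| Toxicity (2.2.2) | Baseline and week-12 MRI required | 11.1.1: all, from registration; 11.2.1: all, from first eribulin; 13.1: treated patients | 11.1.1 and 11.2.1 conflict expressly, 13.1 by implication; 11.1.1 and 11.2.1 also differ from each other |

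**The plan's own figure.** The plan gives no number on this point. The interval that supports its sample size does reproduce: 0.40 ± 1.96 × √(0.4 × 0.6 / 20) = 18.5% to 61.5%. It plays no part below.

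**Size of the OS effect.** Inputs:

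- Background median survival in Section 1.4: 4 to 7.5 months by subtype, and 7 to 18 months with SRS.
- Scan time t: 84 days / 30.4375 = 2.76 months at week 12; 77 / 30.4375 = 2.53 months at the early edge of the window.

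Assumptions: survival is exponential with median m, and death is the only reason for a missing scan.

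Formulas:

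- Share excluded = 1 − 0.5^(t/m).
- Median among those alive at t: solve 0.5^((s − t)/m) = 0.5, which gives s = m + t.
- Expected enrolment to reach 20 with a scan, if patients are replaced = 20 / 0.5^(t/m).

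Example, m = 4 at week 12: 0.5^(2.76/4) = 0.620, so 38% are excluded; the median becomes 4 + 2.76 = 6.76; enrolment is 20 / 0.620 = 32.3.

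| True median (months) | Excluded, week 12 | Reported median | Overstatement | Enrolled for 20 | Missing from OS | Excluded, week 11 | Overstatement, week 11 |
|---|---|---|---|---|---|---|---|
| 4 | 38% | 6.8 | +69% | 32.3 | 12.3 | 35% | +63% |
| 7.5 | 23% | 10.3 | +37% | 25.8 | 5.8 | 21% | +34% |
| 7 (SRS) | 24% | 9.8 | +39% | 26.3 | 6.3 | 22% | +36% |
| 18 (SRS) | 10% | 20.8 | +15% | 22.2 | 2.2 | 9% | +14% |

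Under this model the median is overstated by t itself, about 2.8 months at week 12, whatever the true median. Six-month OS would read 57% instead of 35% for m = 4, and 74% instead of 57% for m = 7.5.

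As a further check, the 13.1-month median of the phase 3 trial described in Section 1.3 gives 14% excluded and a reported median of 15.9 months.

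**Toxicity.** No arithmetic applies, and no figure is claimed.

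**The case against.** The strongest reply is that the OS exclusion is a drafting slip that nobody would carry out. Section 3.6 ties a missing scan only to response, and Section 3.5 follows patients for survival until death. Sections 11.1.1 and 11.2.1 also count patients who progress before the end of cycle 1 as evaluable for response. This makes it plausible that the exclusion is unintended. It does not exempt OS: the statistical section is the broader text, and it is the only one that sets a condition for the secondary analyses.

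On toxicity, one can say that the specific rules in 11.1.1 and 11.2.1 override a general sentence, and that the 13.1 wording merely echoes the objective. The second point is fair, which is why 13.1 is counted as a conflict by implication only. The first still leaves registration versus first dose unresolved.

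On size, the figures are illustrations from background medians. The life-expectancy criterion (4.1.6) and Karnofsky of at least 60 select against early death, so they may be high. In the other direction, 4.1.4 admits patients who have progressed after earlier brain treatment. MRI is also scheduled only while on eribulin (10.2, footnote d), so early stoppers would add exclusions. The counts of missing patients assume replacement continues to 20 evaluable. If only 20 are enrolled, the shares for medians of 4 and 7.5 months give 20 × 0.380 = 7.6 and 20 × 0.225 = 4.5 patients missing.

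Finally, not every patient brought back into OS will have full follow-up. Section 3.4 allows full withdrawal, and Section 8.2.1 treats a patient whose MRI is terminated as withdrawn except for adverse events. That calls for censoring, which Kaplan-Meier handles. None of these points removes the defect.

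**Conclusion.** The concern holds. As written, the plan conditions OS on reaching the week-12 scan, which removes every earlier death and biases the OS curve upward. With exponential survival and death as the only cause of a missing scan, 38% to 23% of patients would be excluded at medians of 4 to 7.5 months, and 24% to 10% at 7 to 18 months. The median would be overstated by about 2.8 months (about 2.5 with a week-11 scan). The direction of the OS bias follows from the rule itself; the size depends on these assumptions.

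For toxicity the finding is limited to contradictory populations, with no claim about the size or direction of any effect. This should be fixed before analysis, but it does not touch the primary success rule.

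**What to change.** Add a sentence to the Evaluability paragraph of Section 13.0 saying that the MRI condition does not apply to OS or toxicity, and that both are analysed in all patients who received at least one dose of eribulin, whether or not a week-12 MRI was done.

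In Section 13.1, state one OS time origin. First dose fits a dosed population, because timing from study entry would again guarantee survival between entry and dosing. If study entry is kept, to match the time-to-progression definition in 11.1.4, the plan should say so. State also that patients who withdraw are censored at last contact.

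Align 11.1.1, 11.2.1, the Evaluability paragraph and 13.1 to one toxicity population.

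The population for the CNS imaging endpoints, the replacement rule and the 20-evaluable design are a separate matter and stay as they are.

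The cost is a few sentences of wording. No new data collection is needed, since survival follow-up (3.5) and adverse events (8.3) are already planned. OS figures, and possibly toxicity figures, will look less favourable. OS and toxicity may include more patients than the 20 evaluable for CNS endpoints, so tables must show both denominators.

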### **13.1 Methods to address the study objectives**

#### **Primary Objective:** CNS PFS at 3 months

We will assess the proportion of subjects without CNS progression at 3 months. We hypothesize that this will be at least 35%. We will generate a Kaplan-Meier curve of CNS PFS and estimate the PFS and 95% CI of the PFS.

#### **Secondary Objective 2.2.1:** Objective RR

We will calculate the proportion (and 95% CI) of the patients with complete and partial response and duration of CNS response.

#### **Secondary Objective 2.2.2:** Toxicity

We will evaluate rates (and 95% CI) of toxicity in patients treated with eribulin.

#### **Secondary Objective 2.2.3:** CBR at 12 weeks

We will sum the proportion of the patients with complete response, partial response and stable disease at 12 weeks (CBR). We will then calculate the proportion (and 95% CI) of patients with CBR at 12 weeks.

#### **Secondary Objective 2.2.4:** Systemic Disease RR

For this objective, we will estimate systemic disease response rate (and 95% CI) and perform a Kaplan-Meier analysis for systemic response in this patient population

#### **Secondary Objective 2.2.5:** Overall Survival

We will generate a Kaplan-Meier curve of OS. Point estimates (and standard error) of OS will be calculated.

## Appendix A

### Performance Status Criteria

ECOG Performance Status Scale		Karnofsky Performance Scale	
Grade	Descriptions	Percent	Description
0	Normal activity. Fully active, able to carry on all pre-disease performance without restriction.	100	Normal, no complaints, no evidence of disease.
		90	Able to carry on normal activity; minor signs or symptoms of disease.
1	Symptoms, but ambulatory. Restricted in physically strenuous activity, but ambulatory and able to carry out work of a light or sedentary nature (e.g., light housework, office work).	80	Normal activity with effort; some signs or symptoms of disease.
		70	Cares for self, unable to carry on normal activity or to do active work.
2	In bed <50% of the time. Ambulatory and capable of all self-care, but unable to carry out any work activities. Up and about more than 50% of waking hours.	60	Requires occasional assistance, but is able to care for most of his/her needs.
		50	Requires considerable assistance and frequent medical care.
3	In bed >50% of the time. Capable of only limited self-care, confined to bed or chair more than 50% of waking hours.	40	Disabled, requires special care and assistance.
		30	Severely disabled, hospitalization indicated. Death not imminent.
4	100% bedridden. Completely disabled. Cannot carry on any self-care. Totally confined to bed or chair.	20	Very sick, hospitalization indicated. Death not imminent.
		10	Moribund, fatal processes progressing rapidly.
5	Dead.	0	Dead.

## Appendix B

### CHILD-PUGH CLASSIFICATION OF SEVERITY OF LIVER DISEASE

Parameter	Points Assigned		
	1	2	3
Ascites	Absent	Slight	Moderate
Bilirubin (mg/dL)	$\leq 2$	2 to 3	$> 3$
Albumin (g/dL)	$> 3.5$	2.8 to 3.5	$< 2.8$
Prothrombin Time			
Seconds over control	1 to 3	4 to 6	$> 6$
INR	$< 1.7$	1.8 to 2.3	$> 2.3$
Encephalopathy	None	Grade 1 to 2	Grade 3 to 4

Modified Child-Pugh Classification of the severity of liver disease according to the degree of ascites, the plasma concentrations of bilirubin and albumin, the Prothrombin time, and the degree of encephalopathy. A total score of 5 to 6 is considered Grade A (well-compensated disease); 7-9 is Grade B (significant functional compromise); and 10 to 15 is Grade C (decompensated disease). These grades correlate with one and two year survival; Grade A – 100% and 65%; Grade B: 80% and 60%; and Grade C – 45% and 35%.
